4.8 Data Quality Assurance

4.8.1 Monitoring, Audits and Inspections

During the investigation, the monitor will have regular contacts with the investigation site. This contact will include visits to confirm that the facilities remain adequate to specified standards and that the investigation site team is carrying out the procedure stated in the CIP and supports the investigator. All data must be accurately recorded in the eCRF. Source data verification (a comparison of data in the eCRF with the subject's hospital/practice and other records at the investigation site) with direct access to records will also be performed.

The monitor, delegate or other Mölnlycke personnel will be available between visits if the investigator or other staff at the site needs information and/or advice.

Authorised representatives of Mölnlycke and/or a Competent Authority (CA) and/or the Ethics Committee (EC)/Institutional Review Board (IRB) may visit the investigation site to perform audits/inspections, including source data verification.

Title: Epaderm01 CIP with Integrated Central Amendment 1

Page 15(21)

Investigation Code Epaderm01 Final Version Approval date 2018-12-10

Central Amendment 1 Approval date 2019-03-14

4.8.2 Training of Staff

The Principal Investigator will ensure that appropriate training relevant to the investigation is given to the medical, nursing and other staff at the site involved and that new information of relevance to the performance of this investigation is forwarded to the staff involved.

4.8.3 Data Management

The Data Management process includes all activities related to data handling regarding:

- Set-up of eCRF and database
- Specification of on-line checks
- Data entry / Data editing
- Export of data from Viedoc to SAS
- Creation of post-entry checks and listings
- Reconciliation of SADE, ADE and DD
- Clean-file process including execution of post-entry checks and listings
- Post clean-file tasks

Viedoc, a web based electronic CRF system, will be used to capture data in this investigation. The eCRF system complies with FDA Title 21 CFR part 11 (ER/ES) requirement.

eCRF training will be given to appropriate personnel before/at initiation of the investigation sites.

Data entry will be performed by investigators and other authorised personnel at the sites. When entering data, on-line checks are incorporated in Viedoc for consistency and validation.

Pharma Consulting Group will support with a helpdesk function taking care of system user questions regarding Viedoc.

When data has been entered, authorised personnel at Mölnlycke can immediately view the data, send queries if necessary and lock eCRF pages when they have been validated.

All data entered in Viedoc will be encrypted. The physical database will be stored in Sweden.

Programs for post-entry checks and data listings will be created and executed for validation of data.

Completeness will be checked by authorised personnel at Mölnlycke so that there are no unexplainable empty fields in Viedoc. This is done to prevent data have being overlooked by personnel entering the data.

A clean-file meeting will be held prior to database lock. All decisions on the evaluability of the data from each individual subject for the statistical analysis must be made and documented before locking the database.

4.9 Statistical Methods and Determination of Sample Size

4.9.1 Analysis populations

Safety population

The safety population includes all subjects who had applied Epaderm Cream.

Intention to treat population

The intention to treat population consists of all subjects attending the baseline visit and meets the Inclusion/Exclusion criteria.

Title: Epaderm01 CIP with Integrated Central Amendment 1

Page 16(21)

Investigation Code Epaderm01 Final Version Approval date 2018-12-10

Central Amendment 1 Approval date 2019-03-14

Per protocol population

An evaluable subject is a subject with a baseline visit and at least one follow-up visit. At the clean file meeting a decision will be made as to which patients to include in the per protocol population. These decisions will be based on the protocol violations affecting skin hydration.

4.9.2 Statistical Evaluation

The results from the investigation period will be presented with descriptive statistics by visit. For continuous variables mean, standard deviation, median, minimum and maximum will be presented and for categorical data number and percentage will be presented.

To evaluate change in skin hydration (Improved Moisturisation) evaluated by subject from baseline to 4 weeks (strongly agree/agree/neither agree nor disagree/disagree/strongly disagree) Sign test will be used. This will be made totally and for each of the three groups (infants, children and adults). This will be presented descriptively.

Change over time for continuous variables will be tested using Wilcoxon signed rank test and for ordered categorical and dichotomous variables signed rank test will be used.

All tests are two-sided with alpha 0.05.

All efficacy analyses will be performed for an ITT/Full analysis set and also for a per protocol population. The safety variables will be studied for the Safety population. All results will be presented totally and for the three groups (infants, children and adults).

Applicable data will be collated into summary tables and figures. Those summary tables and figures will be integrated into the body of the Clinical Investigation Report. Data listings will be prepared for all captured data. The listings will be incorporated into applicable appendices of the Clinical Investigation Report (CIR).

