4. INVESTIGATION PLAN AND PROCEDURES

4.1 *Overall Design*

This investigation is designed as a prospective, non-randomised, single arm clinical investigation. Data will be collected from approximately 120 evaluable subjects, divided into

Title: Epaderm01 CIP with Integrated Central Amendment 1

Page 8(21)

Investigation Code Epaderm01 Final Version Approval date 2018-12-10

Central Amendment 1 Approval date 2019-03-14

three groups of approximately 40 subjects; infants (0-36 months old), children (3-18 years old) and adults (>18 years old), with the following indications: eczema, psoriasis and other dry skin conditions. Each subject will be followed during 4 weeks treatment, with a visit at baseline (visit 1), at 2 weeks (visit 2) and at 4 weeks (visit 3) treatment. An evaluable subject is a subject with a baseline visit and at least one follow-up visit.

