4.3 Procedures and Assessments

Data will be collected at the baseline visit, visit 1 (day 0), at visit 2 (2 weeks, day 14) and at visit 3 (4 weeks, day 28). Collected data will be entered into an eCRF (electronic Case Report Form).

The subject should be instructed not to shower or put on Epaderm Cream before the follow-up visits.

If the subject cannot come to a follow-up visit, the investigator/nurse should collect as much information as possible (at least one documented attempt to reach the subject) and enter this into the eCRF.

Title: Epaderm01 CIP with Integrated Central Amendment 1
Page 9(21)
Investigation Code Epaderm01 Final Version Approval date 2018-12-10
Central Amendment 1 Approval date 2019-03-14

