4.7.3 Performance Measurements and Variables

Primary Endpoint Variable

Subject evaluation of skin moisturisation (hydration) after treatment with Epaderm Cream up to 4 weeks (at 2 and 4 weeks), using a questionnaire (the evaluations should be done on the same affected spot):

- Improved Moisturisation (Strongly agree, Agree, Neither agree nor disagree, Disagree, Strongly disagree)

Secondary Endpoints Variables

1. Subject evaluation of skin softness after treatment up to 4 weeks (at 2 and 4 weeks), using a questionnaire (the evaluations should be done on the same affected spot).
 - Improved Softness (Strongly agree, Agree, Neither agree nor disagree, Disagree, Strongly disagree)
2. Evaluation of the subject's dry skin/xerosis after treatment with Epaderm Cream up to 4 weeks (at baseline, 2 and 4 weeks), by investigator/nurse using "**Overall dry skin score, ODS**". ODS, a scoring scale combining all the major and minor signs of dry skin (xerosis),
0=Absent
1=Faint scaling, faint roughness and dull appearance
2=Small scales in combination with a few larger scales, slight roughness, whitish appearance
3=Small and larger scales uniformly distributed, definite roughness, possibly slight redness and possibly a few superficial cracks
4=Dominated by large scales, advanced roughness, redness present, eczematous changes and cracks
3. Skin hydration using non-invasive device MoistureMeterEpiD (measuring the same treated spot on the skin during baseline and follow-up visits). The device displays percentage water content (%) in the epidermis (appendix G).
4. Subject evaluation (at 2 and 4 weeks), regarding:
 - a. Frequency of application and amount used of Epaderm Cream (please see Accountability 4.5.2)
 - b. Comfort during treatment (Very poor/Poor/Average/Good/Excellent)
 - c. Time of onset of effect, regarding moist and soft skin
 - Immediately
 - Within 2 weeks
 - Within 2 to 4 weeks

Title: Epaderm01 CIP with Integrated Central Amendment 1

Page 13(21)

Investigation Code Epaderm01 Final Version Approval date 2018-12-10**Central Amendment 1 Approval date 2019-03-14**

- Not at all
- d. The overall effect of the investigational device (Very poor/Poor/Average/Good/Excellent)
- e. Did you use the investigational device as a skin cleanser (Yes/No)?

5. Concomitant and previous medication and treatment
6. Number of Adverse Device Effects (ADEs) related to the use of Epaderm Cream during the investigation.

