4.9.3 Determination of Sample Size

The sample size is based on that the investigation is looking at performance of Epaderm Cream measured as Improved Moisturisation evaluated by the subject. The answers will be recoded as three categories strongly agree/agree/neither agree nor disagree/disagree/strongly disagree. The expected distribution of the answers is strongly agree/agree 40%, neither agree or disagree 50% and disagree/strongly disagree 10%. Assuming a power of 80% and using a Sign test a total of approximately 40 subjects is needed in each subgroup (infants, children and adults).

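### Does the lack of a rule for a missing week-4 answer leave the primary sign test undefined?

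*Combined protocol and SAP*

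**What the plan says.** - **Time point of the test.** Section 4.9.2 introduces the sign test in the words "To evaluate change in skin hydration (Improved Moisturisation) evaluated by subject from baseline to 4 weeks". It is done in total and in each of the three age groups, and the results are presented descriptively. The same section presents results by visit.
- **When the question is asked.** Section 4.7.3 defines the primary variable as the subject's rating "after treatment with Epaderm Cream up to 4 weeks (at 2 and 4 weeks), using a questionnaire". The schedule in section 4.3.1 has the subject questionnaire at visits 2 and 3 only.
- **Sets for efficacy.** Section 4.9.2: "All efficacy analyses will be performed for an ITT/Full analysis set and also for a per protocol population".
- **Definition of ITT.** Section 4.9.1: "The intention to treat population consists of all subjects attending the baseline visit and meets the Inclusion/Exclusion criteria". The Full analysis set has no definition of its own.
- **Evaluable subjects.** Section 4.9.1, under the per protocol heading: "An evaluable subject is a subject with a baseline visit and at least one follow-up visit". Section 4.1 uses the same definition for recruitment: "Data will be collected from approximately 120 evaluable subjects".
- **Sample size.** Section 4.9.3: "Assuming a power of 80% and using a Sign test a total of approximately 40 subjects is needed in each subgroup".
- **Missed visits.** Section 4.3: "If the subject cannot come to a follow-up visit, the investigator/nurse should collect as much information as possible". Section 4.8.3 checks for unexplained empty fields and requires decisions on evaluability to be documented before database lock.

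**The concern.** A subject can count towards the 120 with a visit-2 answer only, and a subject can be in the ITT set with no answer at all. The primary test is described at 4 weeks, while the endpoint covers both follow-up visits. No sentence says whether a visit-2-only subject is left out, is represented by the earlier answer, or is counted in some other way, and no denominator is given for the percentage who agree.

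With 40 subjects per age group and half the answers expected to be neutral, the sign test rests on about 20 answers, so two or three subjects can move a p-value across 0.05. The study has one arm, and section 4.8.3 lets sponsor staff see answers once they are entered. A choice made at the clean-file meeting could therefore be made with the answers in view. At stake would be the result in an age group and the reported percentage of subjects who agree.

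**Working it through.** **Inputs.** From section 4.9.3: expected answers 40% agree, 50% neutral, 10% disagree; 80% power; about 40 subjects per group. From section 4.9.2: two-sided alpha 0.05. The number k of evaluable subjects with a visit-2 answer only is not in the documents, so k = 1, 2, 3 per group is an assumption.

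**Step 1: the plan's own figure.** The sign test drops neutral answers. Expected non-neutral answers: 40 × (0.4 + 0.1) = 20. Probability of agreeing among these: 0.4/0.5 = 0.8. The exact two-sided test rejects at 15 or more of 20 (actual alpha 0.041). Power = P(X ≥ 15), X ~ Bin(20, 0.8), = 0.804. The stated 40 per group reproduces. If the number of neutral answers is left random, exact power is 0.742 with 40 answers, 0.718 with 38 and 0.691 with 36. A few missing week-4 answers therefore cost a few points of power in a group.

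**Step 2: which reading the text supports.**

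- The plan assigns efficacy to two sets, not three. Evaluable is a recruitment and per protocol term; it is not a further set for this test.
- The test is at 4 weeks and results are by visit. Section 4.7.3 says when the question is asked, which most naturally gives one result at week 2 and one at week 4.
- Carrying an answer forward appears nowhere.
- A subject with no follow-up has no answer at either visit. Such a subject drops out of the sign test on the week-4 reading and on the last-answer reading alike.
- The item is itself a rating of improvement, so no baseline answer is needed.

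**Step 3: a worst case in one group of 40.** Exact two-sided p = 2 × P(X ≥ larger count), X ~ Bin(m, 0.5), where m is the number of non-neutral answers.

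| k | Week-4 answers only (agree v disagree) | p | Adding k visit-2 answers, all disagree | p |
|---|---|---|---|---|
| 2 | 15 v 4 | 0.019 | 15 v 6 | 0.078 |
| 3 | 15 v 4 | 0.019 | 15 v 7 | 0.134 |

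The counts are the 40/50/10 split of 38 and 37 answers, rounded. If the added answers are neutral, p does not change. If both added answers at k = 2 are agree, the count is 17 v 4 and p falls to 0.007.

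**Step 4: how often the choice would matter.** Let the 40 − k week-4 answers be multinomial with the plan's split. The quantity is the probability that the week-4 test is significant in favour of the cream and the test with the k earlier answers added is not (exact test).

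| Assumed visit-2-only answers | k = 1 | k = 2 | k = 3 |
|---|---|---|---|
| All disagree | 12.0% | 26.0% | 40.0% |
| 30/50/20 (disagreement doubled) | 2.4% | 4.1% | 5.4% |
| 40/50/10 (the plan's split) | 1.2% | 1.9% | 2.2% |

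**Step 5: all ages pooled.** Take 12 of 120 subjects with visit 2 only. The 108 week-4 answers split 43/54/11. Adding 12 disagree answers gives 43 v 11 + 12 = 23, exact p = 0.019. The percentage who agree is 43/108 = 39.8% or 43/120 = 35.8%, depending on the denominator.

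**The case for a change.** The strongest case for a change is that the rule is missing for the only primary endpoint, costs a few sentences, and would remove a choice that can otherwise be made after answers are seen. Descriptive presentation does not settle it, because the plan still sets alpha and sizes each age group for 80% power. Other rules than carrying forward are possible too. With 4 of 40 missing, 14 v 4 gives p = 0.031, while counting the four as disagree gives 14 v 8 and p = 0.286. At 10% missing, that rule would take power in a group from 0.69 to 0.23.

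Part of this stands. The Full analysis set is undefined, neither efficacy set is called primary, the ITT set contains subjects who cannot have an answer, and the denominator is not stated. The clean-file criterion in section 4.9.1 covers protocol violations that affect hydration, not missing answers.

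The rest carries less weight. Counting missing as disagree is a deliberately severe stress test that nothing in the plan suggests, so the gap between it and the observed-answer result does not show that the plan is ambiguous. The same holds for the all-disagree flip rates. Sponsor access to entered data is a feature of open single-arm studies in general. Here it is tempered by documented decisions before lock, by listings of all captured data, and by the instruction to collect what can be collected after a missed visit. Added sensitivity rows, or the moisturisation question at withdrawal, would be extras rather than repairs.

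**Conclusion.** No change follows. The wording is incomplete, but an analyst who follows it as written tests the visit-3 answers that exist, reports week 2 and week 4 side by side, and shows the number of answers at each visit. That gives a sound result. Departing from it by carrying visit-2 answers forward would remove significance in one age group with probability of about 1% to 2% at the plan's own split, or about 2% to 5% with disagreement doubled. Only if every such subject disagreed would it reach 12% to 40%. The pooled result does not turn on it even in an adverse case with 12 of 120, and no decision rule in the plan rests on a single age group. What varies visibly is the denominator, worth 4 percentage points in that pooled example (39.8% against 35.8%), and a reader can see it once the counts are shown.

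This rests on the assumed 1 to 3 visit-2-only subjects per group and on the answer mixes in the table, since the plan gives no rate of missing answers. It also rests on the available text; the appendices could not be checked.

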4.3.1 Schedule of Assessments

Visits	Baseline Visit Visit 1 Day 0	Follow up visit Visit 2 Day 14 (+/-2)	Final visit Visit 3 Day 28 (+/-2)
Informed consent, dated and signed	√		
Inclusion/Exclusion criteria	√		
Subject's age and sex	√		
Relevant medical history	√		
Relevant previous medication or treatment	√		
Concomitant medication/treatment relevant for the investigation	√	√	√
Did the subject have a shower before the visit	√	√	√
Skin disease/condition	√		
Severity of disease/condition	√	√	√
Subject's evaluation of itching in relation to skin condition/diagnosis (VAS scale)	√	√	√
Ongoing flare	√	√	√
Overall Dry Skin Score (ODS)	√	√	√
Body location of target area for skin hydration evaluation	√	√	√
Non-invasive device measuring skin hydration	√	√	√
Subject's treatment compliance		√	√
Subject Questionnaire		√	√
Investigator/nurse Questionnaire	√	√	√
Non-invasive device measuring skin hydration	√	√	√
New relevant medical events		√	√
ADE/DD/SADE		√	√

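### Does Section 4.9.2 leave Improved Softness with a test that cannot show improvement?

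*Combined protocol and SAP*

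**What the plan says.** Section 4.9.2 gives one item its own test. The Sign test is introduced with the words "To evaluate change in skin hydration (Improved Moisturisation) evaluated by subject from baseline to 4 weeks" and is applied in total and in each of the three age groups. A separate sentence covers change over time: Wilcoxon signed rank for continuous variables, while "for ordered categorical and dichotomous variables signed rank test will be used". The level is common to all: "All tests are two-sided with alpha 0.05". The same section opens by promising descriptive statistics by visit, with number and percentage for categorical data.

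Section 4.7.3 defines the softness endpoint as "Subject evaluation of skin softness after treatment up to 4 weeks (at 2 and 4 weeks), using a questionnaire", with the response "Improved Softness (Strongly agree, Agree, Neither agree nor disagree, Disagree, Strongly disagree". In Section 4.3.1 the row "Subject Questionnaire" is ticked at two visits only, whereas the Overall Dry Skin Score, the hydration meter, itching, severity and flare are ticked at all three. Softness therefore has no baseline answer. No section names a test, a visit or a reference value for it.

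**The concern.** Softness is an ordered categorical variable with two post-baseline answers, so the general sentence appears to govern it. The only within-subject change over time available is then week 4 minus week 2. The item already asks whether softness has improved, so that difference shows only whether agreement moved further after week 2.

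The plan itself allows for an early effect. Under "Time of onset of effect, regarding moist and soft skin", Section 4.7.3 offers an immediate effect and an effect within two weeks as possible answers. A cream that had done all its softening by week 2 would then give a null p-value for softness. Softening is one of the effects described for the product in Section 1, and confirming performance is the stated purpose of the investigation.

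**Working it through.** **Inputs.** Section 4.9.3: "The expected distribution of the answers is strongly agree/agree 40%, neither agree or disagree 50% and disagree/strongly disagree 10" per cent, 80% power, Sign test, about 40 subjects per age group. Section 4.9.2: two-sided 0.05. Section 4.1: about 120 subjects in total. The documents give no softness distribution and no correlation between visits. The moisturisation split is borrowed for softness as an assumption.

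**1. The plan's own figure, which shows how an item of this type is meant to be tested.**
- Treat neutral answers as ties. P(agree, given non-neutral) = 0.40 / (0.40 + 0.10) = 0.80, against 0.50 under the null.
- Expected non-neutral answers among 40 subjects: 40 × 0.50 = 20.
- Exact two-sided rule with 20 answers: reject at 15 or more in one direction. Two-sided alpha = 2 × 0.0207 = 0.041. Power = P(X ≥ 15 | 20, 0.80) = 0.804.
- So 20 / 0.50 = 40 subjects give 80%, as stated. Averaged over the random number of ties, exact power is 0.742 at 40 and 0.998 at 120.

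The figure is reproduced by setting agree against disagree, with neutral as the reference. No baseline answer enters the calculation.

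**2. Week 4 against week 2.** Signed rank, answers scored -2 to +2, zeros dropped, normal approximation, simulated with a latent between-visit correlation. Week 4 is 40/50/10 throughout, with 40 subjects.

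| Week-2 split | Correlation 0 | 0.6 | 0.9 |
|---|---|---|---|
| 40/50/10 | about 5% | about 5% | about 5% |
| 30/58/12 | 12% | 19% | about 41% |
| 20/65/15 | 37% | 63% | about 94% |

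The first row is the test's own alpha, because the two visits then have the same distribution. It stays near 5% with 120 subjects. The other rows depend so heavily on the assumed correlation that they bound nothing.

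**3. Week-4 answer against neutral.** A one-sample signed rank test on the same 40/50/10 split with 40 subjects rejects 71-75% of the time. The range comes from letting 25%, 50% or 75% of agree and disagree answers be the strong form. The Sign test gives 74.2%.

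After the three-category recoding of Section 4.9.3, the two tests use the same information. With m non-neutral answers scored +1 or -1, every rank is (m + 1)/2, so the rank sum is the number of agree answers times (m + 1)/2. For 16 agree, 20 neutral and 4 disagree, z = (16 - 4)/√20 = 2.68 and p = 0.007 by the normal approximation; the exact Sign test gives p = 0.012.

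**4. Which reading fits the plan.** Moisturisation and softness share the same stem, the same five answers and the same two visits, and neither has a baseline answer. Section 4.9.2 nonetheless calls the moisturisation answer a change from baseline to 4 weeks. In this plan, then, the answer to an improvement item is itself the change. The general sentence has natural targets elsewhere, in variables measured at baseline: the hydration meter and itching (continuous), dry skin score and severity (ordered), and flare (dichotomous).

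**The case for a change.** The strongest case for a change is that analogy is not text. The moisturisation sentence names one item in parentheses, the general sentence fixes neither visit nor reference value, and two analysts could reach rejection rates of about 5% and 73% from the same data. Reading signed rank as a slip for sign would not supply the missing reference point. One clause settled before database lock would remove the doubt.

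It stands that the softness test is unspecified, and that a week-2-to-week-4 p-value presented as evidence of softening would mislead. It does not stand that this comparison is what the plan means. It requires change to mean one thing for moisturisation and another for its twin item. A third reading is also open, that softness is only described by visit, and under it no misleading p-value arises.

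The remedy is not free either. Section 4.9.2 is part of the CIP, and Section 4.10 notes that an amendment may need ethics committee notification or approval. Confining change tests to variables with a baseline would also remove a legitimate week-2-to-week-4 comparison for comfort and overall effect, which are rated at those visits only.

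**Conclusion.** No change to the plan follows. This is missing detail that an analyst would fill sensibly by treating softness like the primary item: the week-4 answer against neutral, in total and by age group. On that reading the choice between sign and signed rank is immaterial (74.2% against 71-75% with 40 subjects).

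The low figure of about 5% belongs to a reading that the plan's own usage does not favour, and to a case in which nothing moves between visits. Even then the consequence would be limited. The investigation is single-arm, softness has no power claim, success criterion or place in a testing hierarchy, and the week-2 and week-4 percentages would show an early effect whatever test was run. The primary analysis and the sample size are untouched.

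All rejection rates for softness rest on borrowing the moisturisation split and on assumed between-visit correlations. The conclusion rests on the wording of Sections 4.7.3, 4.9.2 and 4.9.3 and does not depend on those rates.
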